5.3.5 Mesopic Contrast Sensitivity (With and Without Glare)

Binocular and monocular (first eye implanted) mesopic contrast sensitivity test (with and without glare) will be conducted at Visit 1(90-180d post 2nd eye implant).

Linear sine grating binocular and monocular mesopic contrast sensitivity testing will be undertaken for spatial frequencies of 12, 6, 3 and 1.5 cycles per degree (cpd) without glare and then with glare using the eVA system. For each subject, the contrast sensitivity function (CSF) at each spatial frequency will be determined (with and without glare) automatically by the eVA system.

Analyses of log contrast sensitivity will be performed for each testing condition (with and without glare) and spatial frequency. [REDACTED]

In addition, for mesopic contrast sensitivity, descriptive summary statistics will be presented by IOL group and 3 mesopic pupil size ranges [≤ 3.0 mm (small), > 3.0 mm to < 4.0 mm (medium), and ≥ 4.0 mm (large)].

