In general, descriptive statistics generated for an endpoint will be based upon the type of parameter (i.e., whether the data is categorical or continuous) being analyzed. For categorical parameters, the statistics used to summarize the data descriptively include sample size, number in the category, and percent in the category. For continuous parameters, sample size, mean, median, standard deviation, minimum, and maximum will be presented. Summaries of logMAR visual acuity may include two-sides 95% confidence intervals for the difference between treatment groups.

A total of 210 subjects will be enrolled (approximately 105 per arm). Assuming a screen failure rate of 9.5%, approximately 190 subjects will be evaluable at Visit 1 (95 per arm). The power estimates for the planned analyses are presented below:

Order	Endpoint	Comparison	Noninferiority Margin	Expected difference	SD	Power
Co	Binocular	Noninferiority	0.10	0.04	0.14	90%
Primary	BCDVA					
Co	Binocular	Superiority	NA	0.085	0.14	> 98%
Primary	DCIVA at					
	66 cm					
1 st	Binocular	Superiority	NA	0.14	0.14	> 99%
Secondary	DCNVA					
	at 40 cm					
2^{nd}	Q1 of	Superiority	NA	0.14	NA	> 96%
Secondary	IOLSAT					
	= NEVER					

	Overall power is estimated based on the assumption that each hypothesis test is independent.
Associated	None
materials	

Table 3–1 Schedule of Study Procedures and Assessments

	Visit 0 (Screening Visit)	Visit 1
	Study Day 0	Study Day 1 to 14 °
Procedure/ Assessment		3 to 6 months (90-180 days) post 2 nd eye implant ^e
Informed Consent	Х	
Demographics	Х	
Medical History ^c	Х	
Concomitant Medications ^c	Х	Х
Inclusion/Exclusion	Х	
Urine pregnancy test ^d	Х	
Photopic Pupil Size	Х	
Slit Lamp Examination	Х	
Tonometry	Х	
Dilated Fundus Examination	Х	
Subjective PCO	Х	
Presence of Posterior Capsulotomy	Х	
IOL Observations	Х	
Absolute IOL Position Change (Tilt/Decentration)	Х	
 Pre-Operative/Operative Information from Chart: Lens model & power IOL calculation method Corneal topography and/or aberrometry (if available) Biometry & keratometry 	X (retrospective)	

	Visit 0 (Screening Visit)	Visit 1
 Predicted residual refractive error Operating surgeon (first eye) 1st eye implanted (OD or OS) Date of Surgery for second eye 		
QUVID questionnaire		Х
IOLSAT questionnaire		Х
Manifest refraction		Х
Binocular BCDVA		X
Binocular DCIVA		X
Binocular DCNVA		X
Binocular Mesopic Contrast Sensitivity (with and without glare)		Х
Monocular Mesopic Contrast Sensitivity (with and without glare) ^b		Х

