10 STUDY PROCEDURES AND ASSESSMENTS

This section describes the procedures and assessments for this clinical study. There are two study Visits in this study.

Visit 0 is the screening visit. Informed consent procedures as well as eligibility are performed at this visit.

Visit 1 will occur 3 to 6 months (90 to 180 days) after the second eye implant of the subject being enrolled. Visit 1 must occur at least one day after the screening visit and it is recommended that is occur a maximum of 14 days after screening. Endpoint assessments and study exit are performed at this visit.

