10.2.5 Photopic Pupil Size: Effectiveness Assessment

During manifest refraction/VA assessment, perform and record photopic pupil size in both eyes at 4 m and record to the nearest 0.5 mm.

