10.2.11 Manifest Refraction: Effectiveness Assessment

Perform and record manifest refraction using technique detailed in the MOP at 4 m. This assessment must be performed by delegated trained masked assessor only.

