10.2.19 Contrast Sensitivity: Safety Assessment

Measure and record both binocular and first eye monocular contrast sensitivity under mesopic lighting conditions with and without glare. This assessment must be performed by delegated trained masked assessor only. Refer to MOP for details.

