5.3.13 Photopic Pupil Size

Photopic pupil size at Visit 0 (screening visit) will be presented as number and percentage in the following categories, respectively: ≤ 3.0 mm (small), > 3.0 mm to < 4.0 mm (medium), and ≥ 4.0 mm (large).

Descriptive statistics including mean, median, standard deviation, number of eyes, minimum, maximum and two-sided 95% confidence interval will be presented by IOL group, separately for first and second implanted eyes.

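### Does the pupil-size grouping of the contrast sensitivity results in SAP 5.3.5 lack a defined measurement, visit and eye?

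*SAP*

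**What the plan says.** SAP 5.3.5 states that the "mesopic contrast sensitivity test (with and without glare) will be conducted at Visit 1(90-180d post 2nd eye implant", and adds that "descriptive summary statistics will be presented by IOL group and 3 mesopic pupil size ranges". The ranges are 3.0 mm or less, above 3.0 but below 4.0 mm, and 4.0 mm or more.

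The visible text on pupil measurement is all photopic:

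- Protocol 10.2.5: "During manifest refraction/VA assessment, perform and record photopic pupil size in both eyes at 4 m and record to the nearest 0.5 mm".
- Protocol Table 3-1 has a row "Photopic Pupil Size" marked at Visit 0 only. SAP Table 10-1 has the same row with the same mark.
- SAP 5.3.13: "Photopic pupil size at Visit 0 (screening visit) will be presented as number and percentage", with the same three ranges as SAP 5.3.5.

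Protocol 10.2.19 describes the contrast sensitivity test without a pupil reading: "Measure and record both binocular and first eye monocular contrast sensitivity under mesopic lighting conditions with and without glare". It refers to the manual of procedures for details. Protocol section 10 requires that "Visit 1 must occur at least one day after the screening visit".

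**The concern.** Three things look unsettled.

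1. **Variable.** Contrast sensitivity is to be grouped by a mesopic pupil size, yet no visible section or schedule row collects one. The cut-points match those for photopic size, so the word may be a slip, or one set of ranges may serve two measurements.
2. **Visit.** Protocol 10.2.5 attaches the photopic reading to an activity scheduled at Visit 1. The schedules and SAP 5.3.13 place it at Visit 0, on a different day.
3. **Eye.** Pupil size is recorded in both eyes, but a binocular test needs one class per subject, and the visible text gives no rule.

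Contrast sensitivity is a named safety objective. If the wrong variable, visit or eye were used, subjects could be placed in the wrong pupil class and the breakdown could be mislabelled. Narrow classes would make this worse.

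**Working it through.** The plan states no figure on this point that could be reproduced. The check sets the passages side by side and lists the values that each class can hold.

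**Visit of the photopic reading**

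| Source | Where it places the reading |
|---|---|
| Protocol 10.2.5 | during manifest refraction and acuity testing |
| Protocol Table 3-1 | Visit 0 |
| SAP Table 10-1 | Visit 0 |
| SAP 5.3.13 | Visit 0 |

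Both schedules mark manifest refraction, BCDVA, DCIVA and DCNVA at Visit 1 only, so protocol 10.2.5 implies Visit 1. No passage writes Visit 1 beside pupil size; the inference takes one step. With at least one day between the visits, one reading cannot satisfy all four sources. Three of the four agree, and the exception is an introductory phrase in a procedure description.

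**Is a mesopic reading missing?** The public text has gaps in the places where one could sit:

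- Protocol numbering skips 10.2.12, 10.2.14, 10.2.16 and 10.2.18.
- SAP Table 10-1 has a row with no label, marked at Visit 1, which is the visit of contrast sensitivity testing.
- The masking text in protocol 9.4 and 11.5 and SAP 1.4 has an item removed between acuity and contrast sensitivity.
- SAP 5.3.5 is redacted just before the sentence on pupil ranges.
- Footnote a under both schedules, on first and second implanted eyes, is attached to no visible row.
- The manual of procedures is not public.

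None of these shows that a mesopic reading is taken. Together they mean that its absence cannot be inferred.

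**Values that each class can hold.** Photopic size is recorded in steps of 0.5 mm (protocol 10.2.5):

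- small, 3.0 mm or less: ..., 2.5, 3.0
- medium, above 3.0 and below 4.0 mm: 3.5 only
- large, 4.0 mm or more: 4.0, 4.5, ...

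A difference of one step between two readings therefore moves every medium subject out of the class (3.5 − 0.5 = 3.0, small; 3.5 + 0.5 = 4.0, large). This holds for SAP 5.3.13. It holds for SAP 5.3.5 only if the grouping variable is on the same 0.5 mm grid, and no recording precision is visible for a mesopic reading. How many subjects would move depends on the pupil distribution, which the documents do not give.

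**Eye.** The monocular test is done on the first implanted eye, which settles that case. SAP 5.3.13 reports first and second eyes separately, so it needs no combining rule. Only the binocular breakdown in SAP 5.3.5 is open.

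**What depends on pupil size.** SAP 5.2 has no formal safety hypotheses. The four hypothesis tests in SAP 4.2 and the power table in SAP 7 use acuity and the spectacle question. The contrast sensitivity analyses by testing condition and spatial frequency do not need the pupil class. What remains is the descriptive breakdown in SAP 5.3.5 and the descriptive table in SAP 5.3.13.

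**The case for a change.** The strongest case for a change is that the visit conflict stands whatever lies behind the redactions. Sites could follow protocol 10.2.5 or the schedule and take the reading on different days, while SAP 5.3.13 expects Visit 0. Visit 0 also includes a dilated fundus examination, and no visible text orders it relative to the pupil reading. Someone working only from the public text would have to guess the variable and, for the binocular test, the eye. The correction would be a few words.

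The inconsistency stands, but its consequence does not follow. The documents give no reason why two undilated photopic readings taken days apart should differ systematically. A reading after dilation would not measure photopic pupil size, so trained staff would take it first. The study team also has what the public reader lacks: the unredacted SAP, the manual of procedures and the case report form. Those fix the variable and visit before any table is programmed, and the eye for the binocular breakdown is chosen when the table shell is drawn up.

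The correction is not quite free. Protocol section 4 requires a written amendment to modify the protocol, although changes that are only logistical or administrative are exempt from prior approval. That is a poor exchange for a descriptive grouping.

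**Conclusion.** No change to the plan is needed. There is one demonstrated slip: protocol 10.2.5 points to Visit 1 for a reading that three other places put at Visit 0. The mesopic grouping in SAP 5.3.5 raises a fair question, but with the text redacted it is not a shown error. The eye for the binocular breakdown is a detail that analysts settle sensibly.

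The effect is confined to descriptive pupil summaries in SAP 5.3.5 and 5.3.13. The effect on hypothesis tests, primary and secondary endpoints and power is nil. The single-value middle class is a limit on how finely the photopic table can be read, and naming the visit or eye would not remove it.

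This rests on two assumptions: that the case report form holds the photopic reading at one identifiable visit, as the schedules imply, and that any photopic reading at Visit 0 is taken before dilation.

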5.3.6 IOP

Intraocular pressure (IOP) measurements will be recorded in mmHg and recorded by the corresponding whole number (e.g., A measurement of 12.8 mmHg or 12.2 mmHg will each be recorded as 12 mmHg). IOP measurements will be conducted at Visit 0 (screening visit).

Descriptive summaries (N, mean, median, standard deviation, standard error, minimum and maximum) of observed values be presented by IOL group, separately for first and second implanted eyes.

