10.2.7 Tonometry: Safety Assessment

Perform tonometry assessment in both eyes according to the to the investigator's standard of care. Record IOP.

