5.2 Safety Hypotheses

There are no formal safety hypotheses in this study. The focus of the safety analysis will be a comprehensive descriptive assessment of safety endpoints listed in Section 5.1.

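### The SAP's whole-number rule for IOP truncates instead of rounding, so mean IOP is biased low wherever a tonometer reads in decimals (minor; descriptive endpoint)

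*SAP*

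**What the plan says.** SAP 5.3.6 sets the recording rule: "Intraocular pressure (IOP) measurements will be recorded in mmHg and recorded by the corresponding whole number". It illustrates the rule with two readings: "A measurement of 12.8 mmHg or 12.2 mmHg will each be recorded as 12 mmHg". It then specifies the output: "Descriptive summaries (N, mean, median, standard deviation, standard error, minimum and maximum) of observed values be presented by IOL group". The two eyes are tabulated apart, by order of implantation. Measurement is at the screening visit only.

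The protocol summary lists mean IOP among the safety endpoints, and Protocol 12.6.1 and SAP 5.1 list IOP. Protocol 10.2.7 is the only protocol text on how it is measured: "Perform tonometry assessment in both eyes according to the to the investigator's standard of care. Record IOP". It names no device, no reading resolution and no whole-number rule. On inference, SAP 5.2 is plain: "There are no formal safety hypotheses in this study".

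**The concern.** Rounding to the nearest whole number makes errors in both directions that largely cancel in a mean. Dropping the decimals makes errors in one direction only, so the mean stays too low however many eyes are measured. The statistic affected is the one the protocol names as the endpoint. The same table also gives a standard error, which would not reflect this error at all. The median, minimum and maximum come from the same truncated values. If decimals are dropped at data entry, the analysis database cannot recover them without going back to source.

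At stake is the accuracy of one descriptive safety summary. No test or claim is at risk.

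**Working it through.** **1. Which rule reproduces the SAP's example?**

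| Rule | 12.8 becomes | 12.2 becomes |
|---|---|---|
| Truncate (drop decimals) | 12 | 12 |
| Round to nearest | 13 | 12 |
| Round up | 13 | 13 |
| SAP 5.3.6 example | 12 | 12 |

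Of these three, only truncation matches.

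**2. Bias in the mean.** Let readings come in steps of h mmHg, and assume that each fractional part 0, h, 2h, …, 1 − h is equally likely. The bias is minus the average fraction dropped, which is −(1 − h)/2.

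| Step h (assumed) | Bias of the mean, mmHg |
|---|---|
| near-continuous | −0.50 (limit) |
| 0.1 | −(1 − 0.1)/2 = −0.45 |
| 0.2 | −(1 − 0.2)/2 = −0.40 |
| 0.25 | −(1 − 0.25)/2 = −0.375 |
| 0.5 | −(1 − 0.5)/2 = −0.25 |
| 1 (whole numbers) | 0 |

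A simulation of 1,000,000 readings at 0.1 mmHg steps (assumed mean 15; SD 2, 3 or 4) gave −0.45 at each SD, so the result hardly depends on the assumed distribution. The SD was almost unchanged (3.00 before truncation and 3.01 after). A single reading at 0.1 mmHg steps can be understated by up to 0.9 mmHg.

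**3. Share of decimal readings.** If a share s of eyes is read in 0.1 mmHg steps and the rest in whole numbers, the bias is −0.45 × s:
- s = 25%: −0.11
- s = 50%: −0.23
- s = 100%: −0.45

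The documents give no value for s.

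**4. Compared with the reported precision.** With 95 subjects per arm (SAP 7) and an assumed SD of 2, 3 or 4 mmHg, the standard error SD/√95 is 0.21, 0.31 or 0.41 mmHg. A bias of 0.45 exceeds each of these, but it arises only if every reading is in 0.1 mmHg steps.

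**5. Difference between arms.** The shift is −0.45 × (share in test arm − share in comparator arm):
- equal shares: 0
- 75% against 25%: −0.45 × 0.50 = −0.23
- 100% against 0%: −0.45

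**6. After the change.** Recording as read leaves no rounding bias. Rounding to nearest at 0.1 mmHg steps leaves +0.05 if halves go up and 0.00 if halves go to the even number. At 0.5 mmHg steps the treatment of halves matters more. Halves up gives (0 + 0.5)/2 = +0.25, as large as the truncation bias but upward. Halves to even, taken over 12.0, 12.5, 13.0 and 13.5, gives (0 − 0.5 + 0 + 0.5)/4 = 0.

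**The case against.** The strongest reply is that nothing turns on this. Safety is descriptive, IOP is taken once with no change from baseline, and the documents set no IOP cut-off that a shift below 1 mmHg could cross. IOP is not among the three safety objectives, which cover adverse events, contrast sensitivity and the visual disturbance questionnaire. All of that stands, and it keeps the severity low.

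A second reply is that the rule is stated openly and applied alike to both arms, perhaps as a deliberate convention. That may be so, but an openly stated rule that only errs downward still gives a mean that is too low. The SAP does not say that the values are truncated or warn the reader of the direction.

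Third, the size rests on facts that the documents do not give. If all sites read whole numbers, the bias is zero. This also stands: 0.5 mmHg is an upper limit, not an expected value. The example does show that its authors had decimal readings in mind.

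Fourth, site entry may be governed by the manual of procedures, which is not available here. That limits what can be said about actual data entry. It does not rescue the SAP sentence.

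A reader might go further and infer a spurious difference between the lens groups. The study is not randomised, tonometry follows each investigator's practice, and balance within sites is recommended but not required. However, such a difference needs the share of decimal readings to differ by arm, and nothing in the documents indicates that it does. The plan also specifies no between-group test or comparison of IOP.

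**Conclusion.** Wrong as written, low severity. The example in SAP 5.3.6 is truncation. Followed literally, it lowers the reported mean IOP by about 0.45 mmHg for readings in 0.1 mmHg steps, 0.25 for 0.5 mmHg steps, at most 0.5 for near-continuous readings, and 0 for whole-number readings. In a mixed sample with 0.1 mmHg steps the bias is about −0.45 times the share of decimal readings.

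This assumes roughly uniform final digits and literal use of the rule. Device, resolution and decimal share are not in the documents, so no single figure can be given for this trial.

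The documents do not support reading this as a threat to the co-primary, secondary or safety conclusions, because none of them uses IOP. A shift between lens groups remains hypothetical.

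**What to change.** In SAP 5.3.6, replace the example with wording such as: *IOP is recorded and summarised as read; if a whole number is required, round to the nearest mmHg (12.8 is recorded as 13, 12.2 as 12).* Recording as read is preferable because it leaves no rounding bias. If whole numbers are kept, add how exact halves are handled; sending them to the even number avoids the upward bias found at 0.5 mmHg steps.

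Make the site recording instruction match, wherever it sits (protocol, manual of procedures or case report form guidance). If truncation is intended, the SAP should say so and note that the mean is biased low for decimal readings.

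The cost is one SAP sentence and a matching entry instruction, with no extra subjects, visits or measurements. If values have already been entered without their decimals, correcting them means going back to source.

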5.3.7 Slit-Lamp Examination

Slit-Lamp Examination is performed at Visit 0 (screening visit). Record any slit lamp findings, absolute IOL position change (tilt and decentration), any IOL observations, any subjective PCO and the subject has the presence of a posterior capsulotomy.

The number and percentage of all abnormal slit lamp examination findings and “worst case” grading for aqueous cells and flare will be presented by IOL group and implanted eye.

A listing will be provided which presents all eyes with an abnormality in any slit-lamp parameter.

5.3.8 IOL observations

IOL observations will be summarized by lens model using descriptive statistics, including frequency (N) and percent of eyes, separately for first and second implanted eyes, at Visit 0 (screening visit). “Other” IOL observations will be summarized and sorted by subject identification (site number, subject number), and by IOL group, separately for first and second implanted eyes.

5.3.9 Absolute IOL position change (Tilt/Decentration)

Descriptive statistics (number and percentages) on eyes with an absolute change at Visit 0 (screening visit) in IOL position category (Tilted, Decentered) will be presented by IOL group, separately for first and second implanted eyes.

In addition, a listing of subjects with absolute IOL position change will be provided.

5.3.10 Subjective posterior capsular opacification (PCO)

Descriptive statistics including number and percentage of eyes at Visit 0 (screening visit) of the “worst case” posterior capsule opacification (including capsulotomy) will be presented by IOL group, separately for first and second implanted eyes.

A listing of eyes with clinically significant posterior capsule opacification, clinically significant posterior capsule opacification requiring YAG or posterior capsulotomy will be presented which includes the posterior capsule opacification or capsulotomy values.

5.3.11 Posterior Capsulotomy

The number and percentage of eyes with posterior capsulotomy at Visit 0 (screening visit) will be presented with a breakdown by IOL group, separately for first and second implanted eyes.

5.3.12 Dilated Fundus Examination

Dilated Fundus Examination is performed at Visit 0 (screening visit).

[figure not shown]
The number and percentage of all dilated fundus examination findings or visualization difficulty will be presented by IOL group, separately for first and second implanted eyes.

[figure not shown]
A listing will be provided which presents all eyes with abnormality or visualization difficulty in any fundus parameter.

5.3.13 Photopic Pupil Size

Photopic pupil size at Visit 0 (screening visit) will be presented as number and percentage in the following categories, respectively: ≤ 3.0 mm (small), > 3.0 mm to < 4.0 mm (medium), and ≥ 4.0 mm (large).

Descriptive statistics including mean, median, standard deviation, number of eyes, minimum, maximum and two-sided 95% confidence interval will be presented by IOL group, separately for first and second implanted eyes.

7 SAMPLE SIZE AND POWER CALCULATIONS

A total of 210 subjects will be enrolled (approximately 105 per arm). Assuming a screen failure rate of 9.5%, approximately 190 subjects will be evaluable at Visit 1 (95 per arm). The power estimates for the planned analyses are presented below:

Table 7-1 Power (%) Under Various Assumptions with Evaluable Sample Size of the difference between Vivity vs Monofocal IOL

Order	Endpoint	Comparison	Noninferiority Margin	Expected difference	SD	Power
Co Primary	Binocular BCDVA	Noninferiority	0.10	0.04	0.14	90%
Co Primary	Binocular DCIVA at 66 cm	Superiority	NA	0.085	0.14	> 98%
1 st Secondary	Binocular DCNVA at 40 cm	Superiority	NA	0.14	0.14	> 99%
2 nd Secondary	Q1 of IOLSAT = NEVER	Superiority	NA	0.14	NA	> 96%

Overall power is estimated based on the assumption that each hypothesis test is independent.

